11 CLINICAL INVESTIGATION ASSESSMENTS

11.1. Investigation Characteristics

❖ The following post-operative parameters will be collected:

- Indication of the surgery with implantation of the lens in the sulcus
- Refraction: objective and subjective
- Best Corrected Visual Acuity (BCVA)
- Pneumotonometry: intra-ocular pressure
- Biometry (using Zeiss IOLmaster 700 SS-OCT) to assess the position of the IOL in relation to the cornea (anterior chamber depth).
- Oculus Pentacam to determine IOL positioning relative to the iris
- SD-OCT: to assess the potential presence of macular edema and RNFL thinning
- Anterior chamber flare meter (Kowa) to determine the presence and quantification of any inflammation or pigment dispersion present in the anterior chamber
- Aberrometry to quantify HOA caused by IOL tilting/decentration

Note that all of the above investigation are non-contact measurements, hence without any risk of adverse events.

❖ Questionnaire about subjective quality of vision at least 6 months postop

- The patient will be asked to grade the quality of vision, at the time of completion, with a score of one to five according to the score system below:

- The questionnaire will be completed during the study visit

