6. OBJECTIVES

The purpose of the study is to collect data that are parameters of post-IOL implantation safety:

- Questionnaire on subjective quality of vision
- Centration and anteroposterior position of the IOL (using biometry)
- Presence and quantification of any inflammation or pigment present in the anterior chamber (flare meter)
- Refractive outcome, with calculation of customized A-constant of the CT Lucia 601 IOL in-the-sulcus and quantification of higher-order aberrations (HOA)
- General safety-parameters:
 - Visual acuity
 - Intra-ocular pressure
 - Presence of macular edema or retinal nerve fiber layer (RNFL) thinning (SD-OCT)
 - Any adverse ophthalmic events

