7. CLINICAL INVESTIGATION DESIGN

Inclusion of the patients will be done post-interventionally: patients that underwent a (usually urgent) vitrectomy to treat a complicated cataract surgery with the implantation of a CT Lucia 601 IOL in the sulcus will be asked to participate in this clinical trial.

For this trial, one additional long-term postoperative visit (at least 6 months after the vitrectomy) will be required besides the standard-of-care visits. During this study visit, besides the standard ophthalmological clinical examination and a questionnaire about subjective vision quality, the following technical examinations will be performed:

1. Biometry (using Zeiss IOLmaster 700 SS-OCT and Oculus Pentacam) to assess the position of the IOL in relation to the cornea (centration and anterior chamber depth).
2. SD-OCT to assess the potential presence of macular edema or retinal nerve fiber layer (RNFL) thinning.
3. Anterior chamber flare to determine the amount of inflammation and pigment dispersion present in the anterior chamber (using Kowa Flare Meter).
4. Quantification of HOA using iDesign Hartmann shack aberrometer

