8.2. Inclusion criteria

- Patients who had implantation of a CT Lucia 601 lens for different reasons:
 - During vitrectomy to treat a complicated cataract surgery and had the implantation of a CT Lucia 601 IOL in the sulcus or patients
 - During phaco surgery with a posterior capsule tear that necessitated the implantation of the implant lens in the sulcus
 - Explantation of an in-the-bag lens and implantation of a CT Lucia 601 as replacement lens (e.g. to treat opacification of the implant lens or intolerance of the implant lens).
- Age : > 18 years
- Signed informed consent
- Preoperative myopia less than 10 diopters
- Implantation of the CT Lucia IOL at least six months earlier

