9.2. Consenting participants

Patients that had an implantation of the CT Lucia 601 at least 6 months ago, will receive a phone call of the study nurse and will receive an informed consent at home. After 2 weeks the study nurse will make a second call to ask the patients to participate in the clinical trial. Per patient, both eyes will be eligible for inclusion in the study. The contralateral eye without CT Lucia 601 will be used to create a control group.

Following the guidelines of the Ethics Review Committee of the World Health Organisation (WHO ERC), potential participant must personally sign and date the latest approved version of the informed consent form before any clinical investigations are performed.

Written and verbal versions of the participant information and Informed consent will be presented to the participants detailing no less than: the exact nature of the clinical investigation; the implications and constraints of the clinical investigation plan; the known side effects and any risks involved in taking part. It will be clearly stated that the participant is free to withdraw from the clinical investigation at any time for any reason without prejudice to future care, and with no obligation to give the reason for withdrawal.

The participant will be allowed as much time as wished to consider the information, and the opportunity to question the Investigator, their GP or other independent parties to decide whether they will participate in the clinical investigation. Written Informed Consent will then be obtained by means of participant dated signature and dated signature of the person who presented and obtained the informed consent. The person who obtained the consent must be suitably qualified and experienced, and have been authorised to do so by the Coordinating/Principal Investigator. A copy of the signed Informed Consent will be given to the participants. The original signed form will be retained at the clinical investigation site.

In case of updates of the participant information and Informed consent the participant must personally sign and date the latest approved version of the informed consent form before any further clinical investigation specific procedures are performed.

For this clinical trial, signature for approval from the patient will be obtained at the appointment in the hospital on the date agreed with the study nurse.

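### Section 11.1 attributes the aberrometer reading to lens tilt or decentration, but it is a whole-eye value and the plan has no step to separate the cornea

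*Combined protocol and SAP*

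**What the plan says.** Higher-order aberrations (HOA) appear in three places in the combined protocol and SAP, and only one of them states a cause.

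- Section 6 (Objectives) places them under refraction: "Refractive outcome, with calculation of customized A-constant of the CT Lucia 601 IOL in-the-sulcus and quantification of higher-order aberrations (HOA"). Lens position is a separate item: "Centration and anteroposterior position of the IOL (using biometry").
- Section 7 (Clinical investigation design) names the device and no cause: "Quantification of HOA using iDesign Hartmann shack aberrometer".
- Section 11.1 (Investigation Characteristics) adds the cause: "Aberrometry to quantify HOA caused by IOL tilting/decentration".

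The Pentacam is used at the same visit, for lens position only. Section 7 pairs it with the IOLMaster "to assess the position of the IOL in relation to the cornea (centration and anterior chamber depth"), and section 11.1 lists "Oculus Pentacam to determine IOL positioning relative to the iris".

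The comparator is set in section 9.2: "The contralateral eye without CT Lucia 601 will be used to create a control group". That eye's surgical history and lens status are not described.

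**The concern.** Section 11.1 presents the reading as the optical effect of a displaced lens. A Hartmann-Shack wavefront is the combined effect of everything the light passes through, so it contains the corneal contribution as well as the lens contribution. Any corneal aberration, whether present before surgery or left by it, would be included in what the plan calls a lens effect.

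The study asks whether this lens can be used safely in the sulcus, and section 6 lists aberrations among the post-implantation safety parameters. Section 13.1 calls the results descriptive but then names group tests, and section 13.3 sets a 5% two-sided level for all analyses. A difference in aberrations between study and fellow eyes could therefore be tested and, on the wording of 11.1, reported as an effect of lens position. If corneal data at a matched pupil diameter are not kept, the two parts cannot be separated later.

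**Working it through.** The plan states no aberration value, standard deviation, threshold or power for this measure, so there is no figure to reproduce. The check is whether any part of the plan isolates the lens contribution.

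**Step 1: what is measured.** For each aberration term, write W = C + I, where W is the whole-eye coefficient, C the corneal part and I the internal part. The internal part is itself I = L + T, where L is the lens's own optical design and T is the effect of tilt or decentration. Section 11.1 gives W the label that belongs to T.

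**Step 2: could the plan remove C?**

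- Corneal measurement: sections 7 and 11.1 give the Pentacam a positional role only. No corneal wavefront or subtraction is planned.
- Baseline: section 7 plans one study visit, at least 6 months after surgery. No preoperative aberration or corneal measurement is listed.
- Adjustment: section 13.1 has no analysis specific to aberrations and no corneal covariate.
- Exclusions: section 8.3 is aimed at uveitis and at conditions affecting lens position. It does not name corneal irregularity.
- Control eye: with s for the study eye and f for the fellow eye, W_s − W_f = (C_s − C_f) + (I_s − I_f). The first bracket vanishes only if the two corneas match. Study eyes enter through vitrectomy for complicated cataract surgery ("During vitrectomy to treat a complicated cataract surgery and had the implantation of a CT Lucia 601 IOL in the sulcus"), capsule tear at phaco surgery, or lens exchange (section 8.2). Nothing in the plan establishes that the fellow cornea is comparable.

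No step removes C.

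**Step 3: can the error be sized?** Only by assumption. If corneal and internal parts are uncorrelated, their RMS values add in quadrature, so a corneal RMS equal to a fraction f of the whole-eye RMS supplies f² of the whole-eye variance:

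| Assumed f | Corneal share, f² |
|---|---|
| 0.2 | 0.04 = 4% |
| 0.5 | 0.25 = 25% |
| 0.8 | 0.64 = 64% |

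The misattributed share could be minor or dominant. This table concerns the whole corneal part within one eye. It does not measure the between-eye bias C_s − C_f.

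**Step 4: is the direction known?** No. Take one term with an assumed W of 0.60 µm.

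- C = +0.20: I = 0.60 − 0.20 = 0.40, so W overstates the internal part (0.60/0.40 = 1.5).
- C = −0.20: I = 0.60 + 0.20 = 0.80, so W understates it (0.60/0.80 = 0.75).

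The sign depends on whether the parts add or partly cancel. This is also why the subtraction must be done term by term and not on RMS values.

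**The case against.** The strongest reply is that this is one causal phrase attached to a secondary descriptive measure. Section 6 asks for aberrations to be quantified, and a whole-eye reading does that. Lens position has its own objective and its own instruments. Section 13.6 leaves the final statistical plan to be agreed before data lock, so there is still time to settle the wording. All of this stands, and it limits the consequence. It does not make the attribution in 11.1 correct.

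Three stronger readings are tempting, and the documents do not support them.

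- *Corneal effects will be counted as lens malposition.* Nothing in the plan classifies position from aberrations. There is no cut-off and no malposition endpoint that uses them.
- *A stated objective goes unanswered.* Section 6 does not ask for aberrations as a consequence of lens position. Only 11.1 makes that link.
- *Surgery has left the study corneas irregular, so the bias runs against the lens.* The documents report no such irregularity. Section 5 mentions incisions as small as 1.8 mm for foldable lenses in general, without giving those used in study eyes, and the visit is at least 6 months later. The fellow eye's history is unstated, so a difference between corneas is possible but not shown.

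A fair objection to the remedy is that subtracting the cornea leaves L as well as T, and that a phakic fellow eye's internal value is that of its natural lens. Internal aberration is thus closer to the lens than the whole-eye value, but it is not a pure measure of tilt or decentration. The fix has to say so.

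**Conclusion.** The point holds for the causal label in section 11.1. As planned, neither whole-eye HOA nor its difference between study and fellow eyes can be attributed to tilt or decentration of the lens. This rests on the general optical principle that a Hartmann-Shack reading includes the cornea, and on the absence from the plan of any corneal separation, baseline or adjustment. It does not depend on surgery having altered the cornea, because corneal aberration that predates surgery would be misattributed in the same way.

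The size and direction of the error cannot be determined from the documents. The figures above are illustrations on assumed values. What is affected is the interpretation of a secondary measure, not the primary safety question and not the direct assessment of lens position. It is worth correcting before analysis, because the correction is cheap and the wording would otherwise invite a causal claim that the data cannot support.

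**What to change.** 1. In section 11.1, delete the words that ascribe the reading to tilt or decentration, and report whole-eye HOA as total optical quality. This costs nothing and is the minimum repair.
2. As the lens-related measure, derive internal HOA term by term: whole-eye coefficients minus corneal coefficients from the Pentacam scan of the same visit, at the same pupil diameter in both eyes. First confirm on site that the scans supply corneal wavefront data and that both eyes are scanned on both devices. The documents do not establish either.
3. In the study eyes, relate internal coma and the other higher-order terms to measured lens decentration. The plan names no separate tilt measurement, so a statement about tilt would need one.
4. State in the analysis plan that internal HOA also includes the lens's own optical design. Record the fellow eye's lens status and show the between-eye contrast by that status, since a phakic fellow eye's value reflects its natural lens.

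If the site confirms the scans, the work is a data export and a subtraction, with no added examination. The downside is added noise from combining two instruments, and the loss of eyes without a valid scan on both devices for this one outcome. The number lost should be reported.

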11.2. Surgical procedure

This is a post-interventional observational study without use of a study drug. There will be no surgical procedure in this study since there is only one single late-postoperative observational visit with technical examinations.

11.3. Safety assessments

The reporting rules under the RD of 15/Jul/1997 and 18/Mar/1999 are not applicable in this post-marketing study.

Medical device incidents will be routinely collected and reported under the national materiovigilance rules at the discretion of the Investigator.

11.4. Adverse events that do not require reporting

Not applicable in this study

12. DATA QUALITY ASSURANCE

12.1. Monitoring, Audit and Inspections

Investigator and the institution(s) will permit trial-related monitoring, audits, EC review, and regulatory inspections (where appropriate) by providing direct access to source data and other documents.

12.2. Training of staff

The Principal Investigator will ensure that appropriate training relevant to the investigation is given to the medical, nursing and other staff at the site involved and that new information of relevance to the performance of this investigation is forwarded to the staff involved.

The staff at the investigational site will sign a confirmation document that they are trained.

12.3. Data Management

In this study, an electronic case report form (eCRF) will be used for data capture. As eCRF, the RedCap platform will be used, which is supported by the UZleuven. A new project with dedicated forms will be created. All changes in the eCRF are logged and time-stamped.

All documents will be stored safely in confidential conditions. On all clinical investigation-specific documents, other than the signed consent, the participant will be referred to by the clinical investigation participant number/code, not by name or EMR number.

All clinical investigation documentation will be kept for 10 years from the clinical investigation plan defined end of clinical investigation point. When the minimum

retention period has elapsed, clinical investigation documentation will not be destroyed without permission from the sponsor.

13. STATISTICS

13.1. Description of statistical methods

The results from this clinical investigation will be presented with descriptive statistics. No hypothesis testing is planned for this investigation.

For continuous variables (ex: age)

In case, the data follow of a normal distribution the T-Test will be applied and the data will be reported as the means and standard deviations by group. Otherwise a signed-rank test of Wilcoxon will be performed and the data will be report as the medians and interquartile ranges.

For count data, the Pearson's Chi² test will be applied to compare the groups and the data will be reported by counts and proportions by group.

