4. CLINICAL INVESTIGATION SUMMARY

Title	CT Lucia 601 IOL implantation in the sulcus
Reference Number (Acronym)	CLuS
Clinical phase	Post-marketing study (phase 4)
Objectives	To perform a retrospective investigation of the CT Lucia 601 IOL implantation in the sulcus

Endpoints	Primary endpoint: determine whether the CT Lucia 601 IOL can be used safely in the sulcus
Design	Non-commercial (academic with study grant), monocentric, post-interventional observational without use of a study drug
Data Collection	A single late-postoperative visit, scheduled ≥ 6 months after the vitrectomy See Study Flow Chart 7.3
Planned Clinical investigation Period	2019-2020
Clinical investigation population	Patients who had an implantation of the CT Lucia 601 lens
Number of Participants	100
Inclusion/Exclusion Criteria	
Inclusion criteria
 
 • Patients with an implantation of a CT Lucia 601 lens for different reasons: 
 ○ During vitrectomy to treat a complicated cataract surgery and had the implantation of a CT Lucia 601 IOL in the sulcus or patients ○ During phaco surgery with a posterior capsule tear that necessitated the implantation of the implant lens in the sulcus ○ Explantation of an in-the-bag lens and implantation of a CT Lucia 601 as replacement lens (e.g. to treat opacification of the implant lens or intolerance of the implant lens). • Age : > 18 years • Signed informed consent • Preoperative myopia less than 10 diopters • Implantation of the CT Lucia IOL at least six months earlier 
Exclusion criteria
 
 • History of uveitis • Ocular pathology or history that could influence the biometry of the effective lens position, such as ocular trauma with zonulolysis, congenital iris- or lens defects etc. • Any eye condition influencing the lens position (to be specified) according to the investigator
Device Name	CT LUCIA hydrophobic C-loop IOL: CT Lucia® 601P (hydrophobic acrylic with heparin coated surface)

Principle Intended Use	All devices are CE marked and used within their claimed intended use. In general, all devices are intended to be used during ophthalmic surgery.
Manufacturer Name	CT LUCIA 601P

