13.2. The number of participants

Given the exploratory nature of the trial, 100 patients will be recruited by group.

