13.3. The level of statistical significance

For all analyses, the level of significance will be 5% two-sided significant level.

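### Section 13.1 rules out hypothesis testing yet prescribes three tests, and its Pearson chi-square does not suit the fellow-eye control

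*Combined protocol and SAP*

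**What the plan says.** Section 13.1 opens by announcing descriptive statistics and stating "No hypothesis testing is planned for this investigation". The rest of the section gives testing instructions:

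- Continuous data, normal: "In case, the data follow of a normal distribution the T-Test will be applied". Whether this is the paired or the independent-samples form is not stated.
- Continuous data, not normal: "Otherwise a signed-rank test of Wilcoxon will be performed".
- Count data: the Pearson chi-square "test will be applied to compare the groups and the data will be reported by counts and proportions by group".

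Section 13.3 adds "For all analyses, the level of significance will be 5% two-sided significant level". Section 13.2 reads "Given the exploratory nature of the trial, 100 patients will be recruited by group".

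Section 13.1 does not say what the groups are. Section 9.2 allows both eyes of a patient into the study and takes the other eye, where it has no CT Lucia 601, as the control.

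The summary in Section 4 gives "Primary endpoint: determine whether the CT Lucia 601 IOL can be used safely in the sulcus". Section 6 says "The purpose of the study is to collect data that are parameters of post-IOL implantation safety" and lists the measurements without marking one as primary. Section 13.5 plans to model whether the primary outcome is missing. Section 13.6 leaves the final statistical plan to be agreed before data lock and before any analysis.

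**The concern.** Two analysts could each follow this text faithfully and write different reports. One would give estimates only; the other would give p-values judged at 5%. Nothing in Sections 13.1 to 13.3 says which instruction yields.

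The tests also do not fit together. The signed-rank test is for paired (or one-sample) data, while Pearson's chi-square is for independent groups. If the groups are the two eyes of the same patients, the chi-square uses the wrong variance. When eyes within a patient are positively correlated, that variance is too large and the test is conservative. In a safety comparison, such a test rejects less often than its stated level implies. Depending on the paired test it is set against, it may also be less able to show an excess of complications in the lens eyes.

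Finally, the missing-data step in Section 13.5 needs one named outcome, and the supplied text does not give one.

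**Working it through.** **1. The contradiction.** This needs no arithmetic. One sentence excludes testing without qualification; three later instructions in the same section require it; Section 13.3 supplies a significance level for all analyses. All are current text.

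**2. Which groups.** Section 9.2 is the only place that describes a control group, and it is the fellow eye. The steps below are conditional on that reading.

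**3. Level of the Pearson chi-square on pairs.** The documents give no event rate, within-patient correlation or number of analysable pairs. Assumed inputs: n = 100 pairs, rate p = 0.10 in both eyes, correlation ρ of 0, 0.2, 0.3 or 0.5, nominal two-sided 5%, no continuity correction.

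Pearson takes the variance of the difference in proportions as 2p(1−p)/n. For pairs it is 2p(1−p)(1−ρ)/n. In large samples the actual level is therefore 2[1 − Φ(1.96/√(1−ρ))]:

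- ρ = 0.2: 1.96/0.894 = 2.19, level about 2.8%
- ρ = 0.3: 1.96/0.837 = 2.34, level about 1.9%
- ρ = 0.5: 1.96/0.707 = 2.77, level about 0.6%

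Exact enumeration over all paired tables gives 5.2% at ρ = 0, then 3.0%, 2.1% and 0.7%, in line with the approximation.

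**4. Power, 10% in one eye against 5% in the other.** Again 100 pairs. The probability that both eyes have the event is p₁p₂ + ρ√[p₁(1−p₁)p₂(1−p₂)]. At ρ = 0.5 this is 0.005 + 0.5 × √(0.09 × 0.0475) = 0.005 + 0.5 × 0.0654 = 0.0377. The discordant cells are then 0.10 − 0.0377 = 0.0623 and 0.05 − 0.0377 = 0.0123. Exact enumeration gives:

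| ρ | Pearson chi-square | Asymptotic McNemar | Exact McNemar |
|---|---|---|---|
| 0.2 | 24.5% | 29.7% | 21.7% |
| 0.3 | 23.0% | 33.1% | 23.9% |
| 0.5 | 19.0% | 45.4% | 30.2% |

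Against asymptotic McNemar, Pearson loses 5.2, 10.1 and 26.4 percentage points. Against exact McNemar it is 2.8 points ahead at 0.2, 0.9 behind at 0.3 and 11.2 behind at 0.5.

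**5. Continuous outcomes.** The signed-rank test fits pairs. If the t-test were run in its independent form with equal SDs, the confidence interval for the mean difference would be wider than the paired one by a factor of 1/√(1−ρ): 1.12, 1.20 and 1.41 at ρ = 0.2, 0.3 and 0.5.

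**6. Primary outcome.** The Section 4 endpoint is a question, Section 6 is a list with no item singled out, and Section 13.5 assumes one outcome. As supplied, the Section 13.5 model has no defined response variable.

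**The case against.** The strongest reply is that this is a descriptive, exploratory study and the sentence in Section 13.1 simply means no confirmatory testing. Section 13.2 does call the trial exploratory, so that is probably the intent. It is not what the sentence says, however, and Section 13.3 applies its level without distinction. The reply shows that the repair is small, not that it is unnecessary.

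The second reply is that pairing is not certain. The example variable in Section 13.1 is age, which cannot differ between two eyes of one patient. Section 13.2 counts patients by group, and the three surgical indications in Section 8.2 could also form groups. This stands as a limit: the criticism of the chi-square holds on the fellow-eye reading, which is the only control the documents describe.

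The third is that the power loss depends on the comparator and on an unknown correlation. That also stands. Against exact McNemar the loss is clear only at 0.5.

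A reader might also infer that a non-significant difference will be taken as proof of safety. The documents nowhere say so. Nor is it right that nothing is linked to safety, since Section 6 describes its whole list as safety parameters. What the supplied text lacks is a named primary variable, and the final plan under Section 13.6 or Appendix B, which was not supplied, may provide it.

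**Conclusion.** The contradiction is established from the text and rests on no assumption: Section 13.1 excludes testing and prescribes it, and Section 13.3 sets a level for it. Neither a later statistical plan nor an appendix would remove it from these sections.

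On the fellow-eye reading, Pearson's chi-square is the wrong test. With positive correlation it falls below its nominal 5%, to between 3.0% and 0.7% over the range examined. The power cost runs from negligible to large, depending on the correlation and on which McNemar test replaces it. These sizes rest on the assumed 100 pairs, the assumed rates and the assumed correlations.

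The unnamed primary outcome is secondary and may be settled elsewhere.

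This should be fixed before any analysis. There is a single non-invasive visit and no interim analysis, so the consequence is limited to how the safety conclusion is read.

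**What to change.** 1. **Section 13.1.** Limit the no-testing sentence to confirmatory tests. Define the groups as eyes with the lens and fellow eyes without it. Make paired differences with 95% confidence intervals the planned result. Label any test exploratory and paired: paired t-test, signed-rank test, and asymptotic or mid-p McNemar in place of Pearson's chi-square.
2. **Section 13.3.** State that two-sided 95% confidence intervals are reported, that any p-value is exploratory and unadjusted for multiplicity, and that a non-significant difference is not evidence of safety.
3. **Section 13.5.** Before any analysis, the sponsor names the variable meant by the primary outcome, chosen from the Section 6 parameters, and states the number of analysable pairs. That number may be below 100 if some fellow eyes also carry the lens. If Appendix B or the final plan already defines the variable, carry that definition across.

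The cost is a text amendment with sponsor review followed by ethics and authority submission (Sections 15.3 and 16.1), plus the sponsor's work in choosing the variable. No new patients or visits are needed.

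### Control eyes are the fellow eyes of the same patients, but Section 13.1 compares count outcomes with Pearson's chi-square, which assumes independent groups, and does not say the t-test is paired

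*Combined protocol and SAP*

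**What the plan says.** Section 9.2 defines the only control group in the plan: "The contralateral eye without CT Lucia 601 will be used to create a control group". It also says "Per patient, both eyes will be eligible for inclusion in the study". Each control eye therefore belongs to a patient who also contributes a study eye.

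Section 13.1 names three tests:

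- Continuous, normally distributed data: "the T-Test will be applied and the data will be reported as the means and standard deviations by group". Paired or unpaired is not stated.
- Continuous, non-normal data: "Otherwise a signed-rank test of Wilcoxon will be performed". When two groups are compared, this is a test for paired data.
- Count data: "For count data, the Pearson's Chi² test will be applied to compare the groups". This is a test for independent groups.

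The same section says "No hypothesis testing is planned for this investigation", while Section 13.3 says "For all analyses, the level of significance will be 5% two-sided significant level". Section 13.2 says "100 patients will be recruited by group" and does not mention pairing. McNemar's test, a paired t-test, a mixed model or any other method for correlated eyes is named nowhere.

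**The concern.** Two eyes of one person share age, systemic disease and much of their ocular history, so their outcomes are likely to be positively correlated. Pearson's chi-square uses only the two group totals and computes the variance of their difference as if the eyes came from different people. With positive correlation that variance is too large, the test is conservative, and its p-values are too large.

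The primary endpoint is whether the lens can be used safely in the sulcus, and the data collected include macular oedema and adverse ophthalmic events. In a safety study a conservative test is not a cautious one, because it errs towards finding no difference between study and control eyes.

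Section 13.1 is also inconsistent with itself. One branch treats the data as paired, one leaves it open, and one treats the eyes as independent.

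**Working it through.** **The plan's own figure.** The 100 patients cannot be reproduced: no effect size, SD, event rate or power is given, only a reference to the exploratory nature of the study. The check therefore concerns the choice of test.

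**Inputs.** From the documents: 100 patients (Sections 8.1 and 13.2), fellow-eye controls (9.2), two-sided 5% (13.3). Assumed: 100 complete pairs, which is an upper bound because any patient with the lens in both eyes, or without an eligible control eye, gives no pair; between-eye correlation phi of 0.1 to 0.5; and the event rates shown below.

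**Step 1. One fixed example.** Take 25 events in 100 study eyes and 15 in 100 control eyes.

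Pearson (no continuity correction): the pooled rate is (25 + 15)/200 = 0.20, so chi-square = (0.25 − 0.15)² / (0.20 × 0.80 × 2/100) = 0.0100/0.0032 = 3.125, p = 0.077. The number of patients with the event in both eyes does not enter.

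McNemar: chi-square = (b − c)²/(b + c), where b counts patients with the event in the study eye only and c those with it in the control eye only. The correlation is phi = (both/100 − 0.25 × 0.15) / √(0.25 × 0.75 × 0.15 × 0.85), with denominator 0.1546.

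| Both eyes | b | c | phi | McNemar chi-square | p, asymptotic | p, exact |
|---|---|---|---|---|---|---|
| 6 | 19 | 9 | 0.15 | 10²/28 = 3.57 | 0.059 | 0.087 |
| 9 | 16 | 6 | 0.34 | 10²/22 = 4.55 | 0.033 | 0.052 |
| 12 | 13 | 3 | 0.53 | 10²/16 = 6.25 | 0.012 | 0.021 |

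Pearson gives p = 0.077 in all three rows.

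**Step 2. Size and power.** Pairs were simulated with P(event in both eyes) = p1·p2 + phi·√(p1·q1·p2·q2), where q = 1 − p, using at least 200,000 data sets per setting. Pearson and asymptotic McNemar were judged against 3.8415, mid-p and exact McNemar at p < 0.05. Results for 100 pairs:

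| | phi 0.1 | phi 0.3 | phi 0.5 |
|---|---|---|---|
| True size at 20% vs 20%, Pearson | 4% | 2% | 0.6% |
| Power at 25% vs 15%, Pearson | 43% | 42% | 40% |
| Same, McNemar asymptotic | 47% | 57% | 71% |
| Same, McNemar mid-p | 44% | 54% | 70% |
| Same, McNemar exact | 38% | 47% | 63% |

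The true size of asymptotic and mid-p McNemar in the same setting is about 4.5% to 5.4%. With 80 pairs, power for Pearson and asymptotic McNemar is 35% vs 39% at phi 0.1 and 30% vs 60% at phi 0.5.

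Rare events at low correlation show little gain. At 5% vs 2%, phi 0.1 and 100 pairs, power is 17% for Pearson, 21% for asymptotic, 17% for mid-p and 10% for exact McNemar.

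**Step 3. The t-test, only if it were run unpaired.** The standard error would be too large by a factor 1/√(1 − rho): 1.05 at rho = 0.1 and 1.83 at rho = 0.7. For a true difference of 0.3 SD and 100 pairs, unpaired versus paired power is 56% vs 60% at rho = 0.1 and 58% vs 84% at rho = 0.5. The plan does not say the test is unpaired, so these figures show only what the missing word could cost.

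**The case against.** The strongest objection is that Section 13.1 never defines the groups. Its example variable is age, which cannot differ between two eyes of one patient, and Section 13.2 speaks of patients per group. If the comparison were between surgical indications, with one eye per patient, Pearson's test would be valid. This stands to the extent that 13.1 must define its groups. But fellow eyes are the only control group the plan names, and the signed-rank fallback fits paired data, so study eye versus fellow eye is the evident comparison.

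Second, a t-test with a signed-rank fallback reads naturally as a paired t-test. That is fair: it is missing wording, not a wrong method, and the conclusion does not depend on it.

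Third, little hangs on these p-values. The study is exploratory, the section says no testing is planned, no decision rule uses a test, and an excess of events would still show in the proportions by group. This limits the impact. It does not remove it, because the same section prescribes tests and 13.3 sets a level for all analyses.

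Fourth, Section 13.6 allows a final statistical plan to be agreed before data lock. That is an opportunity to correct the test, but the present text still prescribes the wrong one.

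Fifth, the gain depends on assumed rates and correlations. The study eye had complicated or replacement surgery, so its complications need not track the fellow eye closely. This stands: at phi 0.1 the gain is slight, and exact McNemar does worse than Pearson there.

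**Conclusion.** The concern holds. For study eye versus fellow eye, Section 13.1 prescribes a test for independent groups on paired data. This is a stated wrong method, not merely a missing detail. The test is conservative whenever the eyes are positively correlated. Under the assumed rates and 100 complete pairs, using Pearson rather than asymptotic McNemar costs about 4 percentage points of power at phi 0.1 (47 − 43), 15 at phi 0.3 (57 − 42) and 31 at phi 0.5 (71 − 40). None of these rates or correlations comes from the documents, and with rare events and low correlation the practical difference is small.

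The damage is confined to exploratory p-values; the planned means, medians, counts and proportions are unaffected. It should be fixed because the correction is cheap and the outcomes concern safety, but it does not undermine the study.

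**What to change.** In Section 13.1:

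1. Define the groups as study eye and fellow eye, paired within patient. Replace Pearson's chi-square with McNemar's test, asymptotic or mid-p, and report the paired risk difference with a 95% CI.
2. State that the t-test is paired, on within-patient differences, with the signed-rank test as fallback. Report the mean or median difference with a 95% CI.
3. Make the complete-pair analysis the main one. If some patients have the lens in both eyes or lack an eligible control eye, add a patient-clustered model (GEE or mixed model) as a supporting analysis.
4. Do not test age or other patient-level variables between the eye groups.
5. Resolve the conflict with Section 13.3. Either delete the sentence that no testing is planned and label the paired tests exploratory, or delete the tests and 13.3 and report paired differences with 95% CIs only.

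The cost is wording and slightly more analysis work, with no extra patients or visits. McNemar's test uses complete pairs only. Its exact version has less power than Pearson at low correlation (38% vs 43% at phi 0.1 in the example), which is why the asymptotic or mid-p version is suggested.
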